#### 2.4. EPFS ACCORDING TO SYMPTOMATIC GROUP

Table 12: Events type PFS

Symptomatic group	Symptomatic (A+C)	Asymptomatic (B)	Total	p value
PFS (event)				
Event				
(PD/death)				
Censored				

1. Pearson's Chi-squared test

Table 13: Median/mean PFS (estimated by Kaplan-Meier)

	Median (months)	CI 95%	Mean	CI 95%
Symptomatic (A+C)				
Asymptomatic (B)				

Table 14: PFS estimated survival ratio

PFS	Events (%, total N)	Patients at risk	% estimated cumulative survival ratio	CI 95%
Symptomatic				
(A+C)				
At 6 months				
At 12 months				
At 18 months				
At 24 months				
Asymptomatic (B)				
At 6 months				
At 12 months				
At 18 months				
At 24 months				

Figure 27: Progression free survival vs Symptomatic group

#### 1. Table of Contents

The database containing the results for the following report was locked on

#### 2. ALL COHORTS

## 2.1. QUALITY OF LIFE QUESTIONARY: EORTC QLQ C-30

All scores are scaled to range from 0-100, even scores based on single items. Be aware that these single-item scales still have only 4 possible values, even though they are transformed to range from 0-100. The scale name and number of items are listed below.

- Global health status/QoL
  - QL Global health status/QoL (revised) (from 2 items)
- Functional Scales (higher is better functioning)
  - PF Physical functioning (from 5 items)
  - RF Role functioning (from 2 items)
  - EF Emotional functioning (from 4 items)
  - CF Cognitive functioning (from 2 items)
  - SF Social functioning (from 2 items)
- Symptom Scales (higher is more symptoms, worse functioning)
  - FA Fatigue (from 3 items)
  - NV Nausea and Vomiting (from 2 items)
  - PA Pain (from 2 items)
- Single-Item Symptom Scores (higher is more symptoms, worse functioning)
  - DY Dyspnoea
  - SL Insomnia
  - AP Appetite Loss
  - CO Constipation
  - DI Diarrhoea
  - FI Financial Difficulties
- QLQ-C30 Summary Score (higher is better functioning, fewer symptoms)
   C30SUMMARY QLQ-C30 Summary Score, composed by taking mean of
   all scores except for QL (Global health status/QoL) and FI (Financial
   Difficulties).

### 2.1.1.GLOBAL HEALTH STATUS/QoL 2.1.1.1. QL - GLOBAL HEALTH STATUS/QoL (REVISED) (FROM 2 ITEMS)

Table 1: Global health status/QoL

Global health status/QoL	N	Mean(SD)	Median(Min-Max)	p-value (wilcoxon test) compared with baseline
Baseline				
w8				
w16				

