## **Quality of Life:**

EORTC QLQ 30 administered at baseline, at week 8 and week 24.

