**Toxicity of the combination after local treatment:** Number of patients with adverse events and serious adverse events, changes in laboratory values, vital signs, electrocardiograms (ECGs), LVEF (MUGA (Multigated Acquisition Scan) / echocardiogram) and assessment of physician, dermatological and ocular examinations graded according to the National Cancer Institute (NCI) Common Terminology Criteria for Adverse Events (CTCAE) v 4.03 after local treatment (after end of local treatment date). It will be studied using descriptive statistics techniques, such as frequency tables and contingency tables. The final statistical analysis of this endpoint is expected to be performed within 6 months after database closure expected at 24 months after last patient inclusion, however interim analysis might be performed when analysing other primary variables.

**Quality of life:** Change from baseline in the global health status score of the EORTC QLQ-C30. The final statistical analysis of this endpoint is expected to be performed within 6 months after database closure expected at 24 months after last patient inclusion, however interim analysis might be performed when analysing other primary variables.

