# 4.7.6.PP - COHORT 2: EXTRACRANIAL PROGRESSION-FREE SURVIVAL (EPFS).

Table 105: Events type PFS

PFS (event)	N	%	95%CI
Censored			
Event (PD/death)			
Total			

Table 106: Median/mean PFS (estimated by Kaplan-Meier)

	Median (months)	CI 95%	Mean	CI 95%
Progression free survival				

Table 107: PFS estimated survival ratio

PFS	Events (%, total N)	Patients at risk	% estimated cumulative survival ratio	CI 95%
At 3 months				
At 6 months				
At 9 months				
At 12				
months				
At 15				
months				

Figure 16: Progression free survival

# 4.8. QUALITY OF LIFE QUESTIONARY: EORTC QLQ C-30. COHORT 2

All scores are scaled to range from 0-100, even scores based on single items. Be aware that these single-item scales still have only 4 possible values, even though they are transformed to range from 0-100. The scale name and number of items are listed below.

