neurological symptoms  1 2 3 4	
1   2   3   4	
1 2 3 4	neurological
2 3 4	
3 4	·
4	
1 Me remort form in values for each variable compared by complete. The first in value	0

1. We report four p-values for each variable, separated by semicolons. The first p-value represents the comparison of the differences between the three assessments. Subsequent p-values correspond to pairwise comparisons: Baseline vs. Assessment 1, Baseline vs. Assessment 3, and Assessment 2 vs. Assessment 3. For dichotomous variables,

Cochran's Q test and McNeiman's test were used. The discrete variable 'number of symptoms' was analyzed with the Friedman and Wilcoxon tests, respectively.

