## 2.2. QLQ-C30 SUMMARY SCORE (HIGHER IS BETTER FUNCTIONING, FEWER SYMPTOMS)

2.2.1.C30SUMMARY - QLQ-C30 SUMMARY SCORE, COMPOSED BY TAKING MEAN OF ALL SCORES EXCEPT FOR QL (GLOBAL HEALTH STATUS/QoL) AND FI (FINANCIAL DIFFICULTIES)

Table 16: QLQ-C30 Summary Score/QoL

QLQ-C30 Summary Score/QoL	N	Mean(SD)	Median(Min-Max)	p-value (wilcoxon test) compared with baseline
Baseline				
w8				
w16				

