#### 4. COHORT B (ASYMPTOMATIC PATIENTS)

Analyses were conducted exclusively on significant variables across the entire sample.

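### Global health status is the protocol's only quality-of-life endpoint, yet 16 QLQ-C30 scores get 32 unadjusted p-values, and significance in the whole sample decides which scores reach the subgroup tables

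*Combined protocol and SAP*

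**What the plan says.** Protocol 10.2 (Study endpoints, Quality of life) names one measure: "Change from baseline in the global health status score of the EORTC QLQ-C30". The synopsis gives the collection times as "EORTC QLQ 30 administered at baseline, at week 8 and week 24", and sections 8.1 and 8.2 agree.

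The quality-of-life report at the end of the combined document has 16 score tables for all cohorts (sections 2.1 and 2.2, Tables 1 to 16). Each has rows for baseline, w8 and w16 and a column headed "p-value (wilcoxon test) compared with baseline". Global health status has the same layout as every other score. The main SAP has a parallel set of 16 tables under "QUALITY OF LIFE QUESTIONARY: EORTC QLQ C-30. COHORT 2" (sections 4.8 and 4.9, Tables 108 to 123).

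Sections 3 and 4 of the quality-of-life report cover symptomatic patients (A+C) and asymptomatic patients (B). Both open with: "Analyses were conducted exclusively on significant variables across the entire sample". Each then tabulates four scores: global health status, emotional functioning, insomnia and the summary score (Tables 17 to 20 and 21 to 24).

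SAP 6.2.1, on neurological symptoms in cohort 2, notes under Table 146: "We report four p-values for each variable, separated by semicolons".

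None of these places states a significance level, a multiplicity adjustment, an order of testing or an exploratory status for the p-values.

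**The concern.** The protocol singles out one score, and the analysis documents give it no precedence among sixteen. With many unadjusted tests, some nominally significant changes are expected even if nothing changed. There is no control arm, so a within-patient p-value is what would be cited in support of a claim that quality of life improved or worsened.

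The subgroup rule makes this worse. A p-value that is merely printed beside a mean can be called descriptive. One that decides which scores are analysed further cannot. The subgroups are also parts of the sample that did the selecting, so a score selected by chance will tend to look confirmed in A+C or B.

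**Working it through.** **The plan's own figure.** The documents state no error rate for quality of life. The one design figure, the response sample size in protocol 10.1, reproduces: n = [(1.645·√(0.4·0.6) + 0.842·√(0.6·0.4)) / 0.2]² = 37.1, so 38; and 38/0.8 = 47.5, so 48. Its 5% one-sided level applies to response only.

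**Counting the tests**
- Scores: global health 1 + functional 5 + symptom scales 3 + single items 6 + summary 1 = 16.
- All cohorts: 16 × 2 visits = 32 p-values. Cohort 2 in the main SAP: another 32.
- A+C: 4 × 2 = 8. B: 4 × 2 = 8.
- Table 146: 8 variables × 4 = 32 p-values, counted here but not modelled.

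**Assumptions.** Two-sided 5% per test, no true change on any score, and a range of correlations between test statistics. The documents give none of these. The summary score cannot be independent of the rest, being "COMPOSED BY TAKING MEAN OF ALL SCORES EXCEPT FOR QL" and financial difficulties, that is, 13 of the other 15.

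**Expected false positives.** 32 × 0.05 = 1.6, whatever the correlation, if each test holds its 5% level.

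**Chance of at least one false positive**
- Independent tests: 1 − 0.95³² = 0.806.
- Correlated tests, three models:

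| Correlation | 32 equally correlated normal statistics | Normal model with the summary built from 13 scores, visits correlated 0.5–0.7 | Item-level signed-rank simulation, 9–12 up to 63 patients |
|---|---|---|---|
| 0 | 81% | 74–77% | 73–78% |
| 0.3 | 68% | 64–68% | 69–73% |
| 0.5 | 52% | 53–56% | 66–72% |
| 0.6 | 43% | 47–50% | not run |
| 0.7 | 35% | 39–42% | 59–64% |
| 0.8 | 26% | not run | not run |

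The correlation in the last column is between latent scores. Measurement error makes the observed change scores less correlated than that, so its rows are not on the same scale as the other two columns.

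- Eight independent tests, as in A+C or B before any selection: 1 − 0.95⁸ = 0.337.

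**Effect of the significance filter.** Take one score at one visit with no true change. Treat the whole-sample statistic as Z = √w·Z₁ + √(1−w)·Z₂, where Z₁ and Z₂ belong to the two subgroups and w is the share of patients in the first. Given |Z| > 1.96, the simulated chance that |Z₁| or |Z₂| also exceeds 1.96 is 65% for a 50/50 split and 68% for 30/70. Without the filter it is 1 − 0.95² = 9.75%. The splits are assumed, and so is a 5% cut-off for the filter.

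**After the fix.** Global health status alone at two visits, unadjusted: at most 9.75% if independent, and 8–9% with visits correlated 0.5 to 0.7. With Holm over the two visits it is at most 5%. Keeping all 32 tests under Bonferroni would require 0.05/32 = 0.0016 per test.

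**The case against.** The best defence is that these are descriptive p-values for a secondary objective in a single-arm phase II trial. The objective is worded broadly as quality of life in both cohorts, so tabulating the whole questionnaire is no departure. Protocol 10.2 already names global health status, and the SAP does not revoke that. All 16 scores are shown with N, mean and median, so nothing is hidden in the all-cohorts tables and a reader can apply 0.0016. Trial success depends on intracranial response only.

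Most of this stands, and it limits the weight of the point. It does not cover sections 3 and 4 of the quality-of-life report, where unadjusted significance determines which scores are analysed at all.

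Some stronger readings do not hold:
- A reader might infer 32 tests in every population. That is true of all cohorts and cohort 2; A+C and B have 8 each.
- A reader might infer that a false quality-of-life finding is more likely than not. That needs the assumed 5% level, no true change on any score and limited correlation; in the normal models it fails from about 0.6 upward.
- A reader might attach a similar error rate to Table 146. The documents give no symptom prevalences, cohort 2 is symptomatic by definition, the four p-values per variable are one overall test with its pairwise follow-ups, and the table stands under other analyses.
- A reader might conclude that the four retained scores are false positives. Nothing in the documents shows that.

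**Conclusion.** The point holds as a reporting and multiplicity weakness in a secondary endpoint. One endpoint is defined; 32 unadjusted p-values are planned for all cohorts and 32 more for cohort 2, with no priority for that endpoint. Scores are then selected for the subgroups by significance in the same patients.

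The size is 1.6 expected false positives per 32 tests. The chance of at least one is 81% if the tests are independent and about 68% to 52% at correlations of 0.3 to 0.5. These figures rest on a two-sided 5% level and no true change, neither of which the documents state. The selection rule is the more serious part, because under it a nominally significant subgroup result for a retained score adds little independent evidence. The change should be made, but the primary response result does not depend on it.

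**What to change.** - Make global health status the only formally tested quality-of-life score, with its two post-baseline visits Holm-adjusted. First reconcile the w16 row of the tables with the protocol's week 24; otherwise the one protected endpoint may rest on a visit at which the protocol does not schedule the questionnaire.
- Report the other 15 scores as exploratory: change from baseline with 95% confidence interval, or p-values adjusted by Holm or for the false discovery rate over the 15 × 2 = 30 tests.
- Remove the significance filter. Either tabulate all scores in A+C and in B, or restrict both subgroups to global health status. Do not describe unadjusted results as significant.
- Label the Table 146 p-values exploratory. The SAP (3.5) and the quality-of-life report (section 1) refer to database closure and lock, so a single symptom variable chosen now could not be presented as pre-specified.

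The cost is SAP wording and minor changes to the output programs, with no new data. The downside is fewer nominally significant quality-of-life results.

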## 2.1.2. FUNCTIONAL SCALES (HIGHER IS BETTER FUNCTIONING) 2.1.2.1. PF - Physical functioning (from 5 items)

Table 2: Physical functioning/QoL

Physical functioning/QoL	N	Mean(SD)	Median(Min-Max)	p-value (wilcoxon test) compared with baseline
Baseline				
w8				

Physical functioning/QoL	N	Mean(SD)	Median(Min-Max)	p-value (wilcoxon test) compared with baseline
w16				

#### 2.1.2.2. RF - ROLE FUNCTIONING (FROM 2 ITEMS)

Table 3: Role functioning/QoL

Role functioning/QoL	N	Mean(SD)	Median(Min-Max)	p-value (wilcoxon test) compared with baseline
Baseline				
w8				
w16				

#### 2.1.2.3. EF - EMOTIONAL FUNCTIONING (FROM 4 ITEMS)

Table 4: Emotional functioning/QoL

Emotional functioning/QoL	N	Mean(SD)	Median(Min-Max)	p-value (wilcoxon test) compared with baseline
Baseline				
w8				
w16				

#### 2.1.2.4. CF - Cognitive functioning (from 2 items)

Table 5: Cognitive functioning/QoL

Cognitive functioning/QoL	N	Mean(SD)	Median(Min-Max)	p-value (wilcoxon test) compared with baseline
Baseline				

Cognitive functioning/QoL	N	Mean(SD)	Median(Min-Max)	p-value (wilcoxon test) compared with baseline
w8				
w16				

#### 2.1.2.5. SF - Social functioning (FROM 2 ITEMS)

Table 6: Social functioning/QoL

Social functioning/QoL	N	Mean(SD)	Median(Min-Max)	p-value (wilcoxon test) compared with baseline
Baseline				
w8				
w16				

## 2.1.3. Symptom Scales (Higher is more symptoms, worse functioning)

2.1.3.1. FA - FATIGUE (FROM 3 ITEMS)

Table 7: Fatigue/QoL

Fatigue/QoL	N	Mean(SD)	Median(Min-Max)	p-value (wilcoxon test) compared with baseline
Baseline				
w8				
w16				

#### 2.1.3.2. NV - Nausea and Vomiting (from 2 items)

Table 8: Nausea and Vomiting/QoL

Nausea and Vomiting/QoL	N	Mean(SD)	Median(Min-Max)	p-value (wilcoxon test) compared with baseline
Baseline				
w8				
w16				

#### 2.1.3.3. **PA - Pain (FROM 2 ITEMS)**

Table 9: Pain/QoL

Pain/QoL	N	Mean(SD)	Median(Min-Max)	p-value (wilcoxon test) compared with baseline
Baseline				
w8				
w16				

## 2.1.4. SINGLE-ITEM SYMPTOM SCORES (HIGHER IS MORE SYMPTOMS, WORSE FUNCTIONING)

2.1.4.1. DY - DYSPNOEA (FROM 1 ITEM)

Table 10: Dyspnoea/QoL

Dyspnoea/QoL	N	Mean(SD)	Median(Min-Max)	p-value (wilcoxon test) compared with baseline
Baseline				
w8				
w16				

#### 2.1.4.2. **SL** - INSOMNIA (FROM 1 ITEM)

Table 11: Insomnia/QoL

Insomnia/QoL	N	Mean(SD)	Median(Min-Max)	p-value (wilcoxon test) compared with baseline
Baseline				
w8				
w16				

#### 2.1.4.3. AP - APPETITE LOSS (FROM 1 ITEM)

Table 12: Appetite Loss/QoL

Appetite Loss/QoL	N	Mean(SD)	Median(Min-Max)	p-value (wilcoxon test) compared with baseline
Baseline				
w8				
w16				

#### 2.1.4.4. CO - CONSTIPATION (FROM 1 ITEM)

Table 13: Constipation/QoL

Constipation/QoL	N	Mean(SD)	Median(Min-Max)	p-value (wilcoxon test) compared with baseline
Baseline				
w8				
w16				

#### 2.1.4.5. DI - DIARRHOEA (FROM 1 ITEM)

Table 14: Diarrhoea/QoL

Diarrhoea/QoL	N	Mean(SD)	Median(Min-Max)	p-value (wilcoxon test) compared with baseline
Baseline				
w8				
w16				

#### 2.1.4.6. FI - FINANCIAL DIFFICULTIES (FROM 1 ITEM)

Table 15: Financial Difficulties/QoL

Financial Difficulties/QoL	N	Mean(SD)	Median(Min-Max)	p-value (wilcoxon test) compared with baseline
Baseline				
w8				
w16				

## 2.2. QLQ-C30 SUMMARY SCORE (HIGHER IS BETTER FUNCTIONING, FEWER SYMPTOMS)

2.2.1.C30SUMMARY - QLQ-C30 SUMMARY SCORE, COMPOSED BY TAKING MEAN OF ALL SCORES EXCEPT FOR QL (GLOBAL HEALTH STATUS/QoL) AND FI (FINANCIAL DIFFICULTIES)

Table 16: QLQ-C30 Summary Score/QoL

QLQ-C30 Summary Score/QoL	N	Mean(SD)	Median(Min-Max)	p-value (wilcoxon test) compared with baseline
Baseline				
w8				
w16				

#### 3. COHORTS A-C (SYMPTOMATIC PATIENTS)

Analyses were conducted exclusively on significant variables across the entire sample.

3.1.1.GLOBAL HEALTH STATUS/QoL
3.1.1.1. QL - GLOBAL HEALTH STATUS/QoL (REVISED) (FROM 2 ITEMS)

Table 17: Global health status/QoL

Global health status/QoL	N	Mean(SD)	Median(Min-Max)	p-value (wilcoxon test) compared with baseline
Baseline				
w8				
w16				

## 3.1.2. FUNCTIONAL SCALES (HIGHER IS BETTER FUNCTIONING) 3.1.2.1. EF - EMOTIONAL FUNCTIONING (FROM 4 ITEMS)

Table 18: Emotional functioning/QoL

Emotional functioning/QoL	N	Mean(SD)	Median(Min-Max)	p-value (wilcoxon test) compared with baseline
Baseline				
w8				
w16				

3.1.3. SINGLE-ITEM SYMPTOM SCORES (HIGHER IS MORE SYMPTOMS, WORSE FUNCTIONING)
3.1.3.1. SL - INSOMNIA (FROM 1 ITEM)

Table 19: Insomnia/QoL

Insomnia/QoL	N	Mean(SD)	Median(Min-Max)	p-value (wilcoxon test) compared with baseline
Baseline				
w8				
w16				

## 3.2. QLQ-C30 SUMMARY SCORE (HIGHER IS BETTER FUNCTIONING, FEWER SYMPTOMS)

3.2.1.C30SUMMARY - QLQ-C30 SUMMARY SCORE, COMPOSED BY TAKING MEAN OF ALL SCORES EXCEPT FOR QL (GLOBAL HEALTH STATUS/QoL) AND FI (FINANCIAL DIFFICULTIES)

Table 20: QLQ-C30 Summary Score/QoL

QLQ-C30 Summary Score/QoL	N	Mean(SD)	Median(Min-Max)	p-value (wilcoxon test) compared with baseline
Baseline				
w8				
w16				

#### 4. COHORT B (ASYMPTOMATIC PATIENTS)

Analyses were conducted exclusively on significant variables across the entire sample.

## 4.1.1.GLOBAL HEALTH STATUS/QoL 4.1.1.1. QL - GLOBAL HEALTH STATUS/QoL (REVISED) (FROM 2 ITEMS)

Table 21: Global health status/QoL

Global health status/QoL	N	Mean(SD)	Median(Min-Max)	p-value (wilcoxon test) compared with baseline
Baseline				
w8				
w16				

## 4.1.2. FUNCTIONAL SCALES (HIGHER IS BETTER FUNCTIONING) 4.1.2.1. EF - EMOTIONAL FUNCTIONING (FROM 4 ITEMS)

Table 22: Emotional functioning/QoL

Emotional functioning/QoL	N	Mean(SD)	Median(Min-Max)	p-value (wilcoxon test) compared with baseline
Baseline				
w8				
w16				

## 4.1.3. SINGLE-ITEM SYMPTOM SCORES (HIGHER IS MORE SYMPTOMS, WORSE FUNCTIONING)

4.1.3.1. SL - INSOMNIA (FROM 1 ITEM)

Table 23: Insomnia/QoL

Insomnia/QoL	N	Mean(SD)	Median(Min-Max)	p-value (wilcoxon test) compared with baseline
Baseline				
w8				
w16				

## 4.2. QLQ-C30 SUMMARY SCORE (HIGHER IS BETTER FUNCTIONING, FEWER SYMPTOMS)

4.2.1.C30SUMMARY - QLQ-C30 SUMMARY SCORE, COMPOSED BY TAKING MEAN OF ALL SCORES EXCEPT FOR QL (GLOBAL HEALTH STATUS/QoL) AND FI (FINANCIAL DIFFICULTIES)

Table 24: QLQ-C30 Summary Score/QoL

QLQ-C30 Summary Score/QoL	N	Mean(SD)	Median(Min-Max)	p-value (wilcoxon test) compared with baseline
Baseline				
w8				
w16
